8.2 Participant demographics/other baseline characteristics

Participant demographic and baseline characteristic data to be collected on all participants include age, sex, race, ethnicity, and source of patient referral. Any relevant medical history including surgical/medical procedures, protocol solicited medical history, and/or current medical conditions before obtaining informed consent will be recorded in the Medical History eCRF. A detailed medical history (including cardiovascular and other conditions relevant to the study population to be enrolled) and current medical conditions present, including the presentation and management of index MI event will also be recorded. Where possible, diagnoses and not symptoms, will be recorded. All medications and relevant medical histories will be recorded on the corresponding eCRFs.

8.3 Efficacy

The primary efficacy variables are the following:

- 1. Percent change from baseline in LDL-C
- 2. Achieving LDL-C < 70 mg/dL (yes, no)

The secondary efficacy variables are the following:

- Absolute change from baseline in LDL-C
- 2. Average percent change from baseline in LDL-C levels to each post-baseline visit
- 3. Average absolute change from baseline in LDL-C levels to each post-baseline visit
- 4. Achieving LDL-C < 100 mg/dL (yes, no) (among the subset of participants with LDL-C ≥ 100 mg/dL at baseline)
- 5. Achieving \geq 50% reduction from baseline in LDL-C (yes, no)
- 6. Achieving LDL-C < 55 mg/dL (yes, no)
- 7. Percent change from baseline in apoB
- 8. Absolute change from baseline in apoB
- 9. Percent change from baseline in VLDL
- 10. Absolute change from baseline in VLDL
- 11. Percent change from baseline in non-HDL-C
- 12. Absolute change from baseline in non-HDL-C
- 13. Percent change from baseline in total cholesterol
- 14. Absolute change from baseline in total cholesterol
- 15. Percent change from baseline in Lp(a)
- 16. Absolute change from baseline in Lp(a)
- 17. Percent change from baseline in HDL-C
- 18. Absolute change from baseline in HDL-C
- 19. Percent change from baseline in triglycerides
- 20. Absolute change from baseline in triglycerides
- 21. Intensity of lipid-lowering therapy (decrease in dose, no change in dose, increase in dose)
- 22. Proportion of days covered (total number of days on either statin, ezetimibe, or PCSK9 inhibiting monoclonal antibody therapies divided by total number of study days)
- 23. Discontinuation of statin therapy (i.e., no statin use ≥ 30 days before the end-of-study visit) (yes, no)

The exploratory efficacy variables are the following:

8. Cardiovascular death (yes, no)

- 9. Non-fatal MI (yes, no)
- 10. Resuscitated cardiac arrest (yes, no)
- 11. Non-fatal ischemic stroke (yes, no)
- Composite MACE (cardiovascular death, non-fatal MI, resuscitated cardiac arrest, or non-fatal ischemic stroke) (yes, no)

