$$H_0: [\pi_1/(1 - \pi_1)]/[\pi_0/(1 - \pi_0)] \leq 1 \text{ versus } H_A: [\pi_1/(1 - \pi_1)]/[\pi_0/(1 - \pi_0)] > 1$$

Primary efficacy variable 2 will be analyzed at each post-baseline visit using a logistic regression model with treatment and baseline LDL-C as explanatory variables (Stokes et al. 2012). The odds ratio, two-sided 97.5% confidence interval for the odds ratio, and p-value based on the fitted model will be reported. If the p-value based on a two-sided test for inclisiran + usual care versus usual care at Day 330 is < 0.025 and the corresponding odds ratio is greater than 1, statistical significance in favor of inclisiran + usual care is shown. In case of non-

convergence of a logistic regression model, the model will be updated to use Firth's penalized likelihood method (Firth 1993). If the model using Firth's method still shows convergence issues then the baseline LDL-C covariate may be removed from the model. Two-sided 97.5% confidence intervals for the proportion of participants who achieve LDL-C < 70 mg/dL in each treatment group will be calculated, using the normal approximation to the binomial distribution.

The primary analysis of primary efficacy variable 2 will be based on the FAS. The primary analysis of this variable will be repeated for the Per-Protocol Set, Restricted Set 1, and Restricted Set 2.

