2.12 Other Exploratory analyses

The exploratory efficacy variables are the following:

8. Cardiovascular death (yes, no)
9. Non-fatal MI (yes, no)
10. Resuscitated cardiac arrest (yes, no)
11. Non-fatal ischemic stroke (yes, no)
12. Composite MACE (cardiovascular death, non-fatal MI, resuscitated cardiac arrest, or non-fatal ischemic stroke) (yes, no)

[REDACTED]

[REDACTED]

[REDACTED]

Exploratory efficacy variables 8-12 will be summarized descriptively by total number of events and number and percentage of subjects with any event for each treatment group. In addition, a time-to-event analysis will be carried out. Time to first occurrence of any event in the composite MACE as well as time to first occurrence of each of its components will be derived as study day of onset of the corresponding TEAE, imputing for partially missing dates as needed. Adverse events with missing onset date will not be considered in the time-to-event analysis. Cox proportional hazards models will be used to estimate the corresponding hazard ratios of inclisiran + usual care over usual care with associated 95% confidence intervals. Treatment and baseline LDL-C will be used as explanatory variables in the Cox proportional hazards models. Observation time for participants without the respective event will be censored at their end of study date (date of last participation) or date of death, as applicable.

[REDACTED]

[figure not shown]
[REDACTED]

[REDACTED]

Table 2-6 MACE Definitions (using TEAEs only)

Category	Details
Cardiovascular death	(1) Fatal SAEs in "Cardiac disorders" SOC (2) Fatal SAEs in "General disorders and administration site conditions" SOC: PTs "Death", "Sudden cardiac death", "Cardiac death", "Apparent death" (3) Central nervous system haemorrhages and cerebrovascular accidents (HLT), fatal events only
Non-fatal MI	Myocardial infarction (SMQ, broad and narrow search), non-fatal events only, excluding PT "Blood creatine phosphokinase increased"
Resuscitated cardiac arrest	PT "Cardiac arrest", non-fatal events only

Non-fatal ischemic stroke	PT "Ischaemic stroke", non-fatal events only
---------------------------	--

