2.13 Interim analysis

After all participants complete their baseline visit, the demographic and baseline characteristics may be summarized to help design new studies. No analysis will be performed using post-baseline data. Thus, there is no need to adjust the level of significance for such interim analysis of baseline data.

3 Sample size calculation

The sample size was calculated for the two primary efficacy variables with adjustment for multiple testing by using the Bonferroni procedure.

For primary efficacy variable 1, i.e., percent change from baseline in LDL-C, the standard deviation is assumed to be 40, partly based on the results from ORION-10 and ORION-11 clinical trials and considering that the standard deviation will likely be larger in this trial since changes in lipid-lowering therapy are allowed in both treatment groups. An expected mean treatment difference of 15 is assumed, which is smaller than the mean difference observed in the Phase III trials, to account for 1) potential lower utilization of background lipid-lowering therapy in the inclisiran + usual care treatment group compared to the usual care treatment group, and 2) the ability to add non-statin lipid lowering therapy in the usual care treatment group. A z-test, an allocation ratio of 1:1, and a two-sided significance level of 0.025 were also used in the calculation of sample size.

[Table 3-1](#) considers total sample sizes for expected mean treatment differences of 10, 15, and 20, and powers of 0.85 and 0.90 (nQuery Version 8.4.1.0). From [Table 3-1](#), an expected mean treatment difference of 15 (based on means of 40 and 55 at Day 330 in the usual care and inclisiran + usual care treatment groups, respectively) and a power of 0.85 were chosen to provide a total sample size of 306 participants.

Table 3-1 Sample Size Calculations for Percent Change from Baseline in LDL-C

Mean treatment difference	Power = 0.85	Power = 0.90
10	688	796
15	306	354
20	172	200

For primary efficacy variable 2, i.e., achieving LDL-C < 70 mg/dL (yes, no), a z-test, an allocation ratio of 1:1, and a two-sided significance level of 0.025 were used in the calculation of sample size.

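### SAP 2.12 plans a Cox hazard ratio for every MACE component but has no rule for sparse events, so at least one rare component is likely to have no finite hazard ratio unless event rates are very high

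*Protocol*

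**What the plan says.** Protocol 8.3 and 12.6 list cardiovascular death, non-fatal MI, resuscitated cardiac arrest, non-fatal ischemic stroke and composite MACE as yes/no exploratory variables (for example "Resuscitated cardiac arrest (yes, no"). The protocol names no Cox model for them.

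The model comes from SAP 2.12, which derives time to first event for the composite and for each component. It states that "Cox proportional hazards models will be used to estimate the corresponding hazard ratios of inclisiran + usual care over usual care", with associated 95% confidence intervals, and that "Treatment and baseline LDL-C will be used as explanatory variables in the Cox proportional hazards models". Event numbers and percentages by arm are planned as well. SAP Table 2-6 defines two components by a single preferred term each, non-fatal only: cardiac arrest and ischaemic stroke. Non-fatal MI is a broad and narrow standardized query. Cardiovascular death covers several groups of fatal events.

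SAP 2.5.2 does plan for models that fail. For the MMRM, compound symmetry replaces the unstructured matrix. For logistic regression, "the model will be updated to use Firth's penalized likelihood method", and baseline LDL-C may then be dropped. The SAP document history shows that the same amendment added this non-convergence methodology and the MACE time-to-event analyses. The visible text has no counterpart for Cox regression.

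**The concern.** A Cox model estimates the treatment coefficient by comparing who has events in each arm. If one arm has none, the partial likelihood keeps rising as the coefficient moves away from zero and never reaches a maximum. The program stops at an arbitrary point and prints a hazard ratio near 0 or a very large one, with a standard error that carries no information. If neither arm has an event, there is nothing to estimate.

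With this sample size and follow-up, the two single-term components can be expected to have very few events. A printed hazard ratio of 0.00 could be misread as benefit, and a huge one as harm. Without a rule, the team must also decide what to do after seeing the data of an open-label trial.

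**Working it through.** **Size of the arms.** The SAP's sample size section (Section 3) gives the inputs: "the standard deviation is assumed to be 40"; "An expected mean treatment difference of 15 is assumed"; "a two-sided significance level of 0.025 were also used in the calculation of sample size"; "a power of 0.85 were chosen to provide a total sample size of 306 participants".

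- Per arm: 2 × (2.2414 + 1.0364)² × 40² / 15² = 152.8, so 153, and 306 in total. This matches the plan.
- With 20% loss: 306 / 0.80 = 382.5, so 383, or 384 with equal arms. This also matches, and gives 192 per arm.

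The calculation concerns LDL-C only. Neither document states a MACE rate, event count or power, so the risks below are **assumptions**, shown over a range.

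**Chance of events in one arm only.** Let r be the 330-day risk, equal in both arms, and q = (1 − r)^192 the chance that an arm has no event. Then:

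- P(events in exactly one arm) = 2q(1 − q): hazard ratio 0 or infinite.
- P(no events in at least one arm) = 1 − (1 − q)²: no finite hazard ratio, including no events at all.

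| r per arm | Expected events, both arms | HR 0 or infinite | No finite HR |
|---|---|---|---|
| 0.25% | 1.0 | 47% | 85% |
| 0.5% | 1.9 | 47% | 62% |
| 1% | 3.8 | 25% | 27% |
| 1.5% | 5.8 | 10% | 11% |
| 2% | 7.7 | 4% | 4% |
| 3% | 11.5 | 0.6% | 0.6% |

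Put in terms of total events D with no treatment effect, P(all in one arm) = 2 × 0.5^D: 50% for D = 2, 25% for 3, 12.5% for 4 and 6% for 5.

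**Across the four components**, treated as independent: P(at least one) = 1 − product of (1 − p).

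| Scenario | Assumed risk: CV death / MI / arrest / stroke | At least one HR 0 or infinite | At least one without a finite HR |
|---|---|---|---|
| Low | 0.5 / 2 / 0.25 / 0.25% | 86% | 99% |
| Mid | 1 / 3 / 0.25 / 0.5% | 79% | 96% |
| High | 2 / 5 / 0.5 / 1% | 62% | 73% |
| Extreme | 3 / 8 / 1 / 2% | 28% | 30% |

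Worked for the mid scenario, the chance that no component is affected is 0.7518 × 0.9942 × 0.5280 × 0.5279 = 0.208, so at least one is 79%. Exactly one is 0.208 × (0.2482/0.7518 + 0.0058/0.9942 + 0.4720/0.5280 + 0.4721/0.5279) = 0.442, which leaves 35% for two or more. The same sum gives 47% (low), 14% (high) and 1% (extreme).

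**Which outcomes are exposed.** At the assumed MI risks, from 2% upwards, the chance for non-fatal MI is 4% or less. If component risks are simply added, the composite risk is 3% in the low scenario and 4.75% in the mid, so its chance is at most 0.6%.

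**Check of the divergence.** An ordinary Cox fit was run with 192 simulated participants per arm, three events all in the control arm, and an LDL-C covariate. The treatment coefficient went from −11 after 10 iterations to −45 after 200, and its standard error from 156 to 3.3 × 10⁹. With the LDL-C coefficient held at zero, the log partial likelihood rose from −17.844 at coefficient 0 to −15.757 at −10 and was still rising marginally at −15.

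**The case against.** The case for leaving the text alone has several parts.

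- **The rates are assumed.** This is correct. Participants are recruited soon after an ACS and described as being at high risk, and MI and cardiovascular death are defined broadly. At extreme rates the chance is 28%, so a degenerate result is no longer likely. A reader might infer that the trial is bound to see only a handful of events; the documents do not say so.
- **Several component hazard ratios will be artefacts.** A reader might infer this, but it does not follow. Two or more degenerate components has a chance below one half in every scenario.
- **These are the only comparative clinical-outcome results.** They are not. The composite hazard ratio, the counts and percentages by arm, and the risk ratios with 95% intervals for serious treatment-emergent events (SAP 2.7.1) are also planned. A hazard ratio of 0.00 would appear beside its counts, which limits the scope for misreading.
- **The SAP does not prescribe unpenalized estimation or Wald limits.** This is true. It says only Cox models with 95% intervals, so a penalized fit would comply. The gap is an unspecified rule rather than a wrong method. It still matters, because the ordinary fit is the plain reading and fails in a foreseeable case.
- **Parts of SAP 2.12 are blacked out.** A rule there cannot be excluded. The visible Cox paragraph reads as complete and contains none.
- **The endpoints are exploratory.** No success criterion or sample size depends on them. This stands and sets the weight of the point.

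**Conclusion.** The point holds for the rarest components. Under the stated plan, the chance that at least one component hazard ratio is 0 or infinite is about 62–86% over low to high assumed risks, and about 28% at extreme ones. These figures assume 192 per arm, equal risk in both arms, independent components and risks that the documents do not give. Resuscitated cardiac arrest and non-fatal ischemic stroke are the main candidates, with cardiovascular death possible at lower rates. Non-fatal MI and the composite are largely unaffected, so nothing here argues for changing their analysis as a matter of course. The protocol's endpoint list is sound; the gap is in SAP 2.12 alone. This is a cheap improvement that does not touch the primary conclusions.

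**What to change.** Add to SAP 2.12:

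1. For any component with fewer than a pre-specified number of events in total (for example 5), or with no events in one arm, report only the counts and percentages by arm already planned, without a hazard ratio.
2. If a remaining Cox model does not converge or its likelihood is monotone, use Firth-penalized partial likelihood with profile-likelihood 95% limits, mirroring the logistic fallback in SAP 2.5.2.

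A minimum-size rule is already SAP practice: subgroup results are shown only with at least 10 participants (SAP 2.2.1). The number 5 is a convention that the team may replace, provided it is fixed before the data are seen. At 5 events, a split entirely into one arm has a chance of 6% with no treatment effect.

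The cost is a sentence or two and a standard software option. The price is that the rarest exploratory components get no hazard ratio. With total events binomial (384, r), fewer than 5 occur in 99.7% of trials at r = 0.25%, 95% at 0.5%, 66% at 1% and 12% at 2%. At such counts a hazard ratio would say little beyond the counts themselves.

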8.3.1 LDL-cholesterol

The primary efficacy assessment will be LDL-C, from which the two primary efficacy variables (percent change from baseline in LDL-C; achieving LDL-C < 70 mg/dL [yes, no]) are derived. Samples for LDL-C will be collected at screening and on visits 1, 2, 3, 4 and 5 (Table 8-1).

After randomization, the treating physician will not have access to LDL-C values obtained as part of the study.

8.3.2 Other lipoprotein measures

Other efficacy assessments will include measurement of Apolipoprotein B, Lp(a), VLDL, non-HDL-C, total cholesterol, triglycerides, HDL-C, discontinuation of statin therapy and changes in other background lipid lowering therapies. Samples for these additional efficacy biomarkers will be collected at Visits 1, 2, 3, 4 and 5 (Table 8-1). Assessment of lipid lowering medications will be collected at each of these visits and will be complemented, when possible, by any additional information obtained from EHR and claims data to verify adherence to background therapy.

8.3.3 Appropriateness of efficacy assessments

The assessment of LDL-C and other lipoproteins are standard in both clinical practice and in trials evaluating the efficacy of lipid-modifying therapies in patients following a recent ACS with an elevated LDL-C (Grundy et al 2019). LDL-C reduction, which is an effect of the mechanism of action of inclisiran, is a well-defined biomarker that is routinely assessed in clinical trials and is the primary efficacy variable of the study. Laboratory and other assessments related to the secondary and exploratory objectives are in line with the expected efficacy of inclisiran. Utilization of other lipid lowering therapies, including, but not limited to, statins, is another important component to LDL-C efficacy and assessment of their use, including adherence, will be collected to further evaluate the effectiveness of inclisiran in this study.

8.4 Safety

Safety assessments will consist of monitoring and recording of all adverse events and serious adverse events, evaluation of hematology, blood chemistry and urine values, regular measurement of vital signs and the performance of physical examinations.

As per Section 4.6, during a Public Health emergency that limits or prevents on-site study visits regular phone or virtual calls should occur for safety monitoring and discussion of the participant's health status until the participant can again visit the site. If a participant cannot visit the site to have pregnancy tests done, a home urine pregnancy test kit may be used. Participants can perform the urine pregnancy test at home at the time of the scheduled visit and report the result to the site, or a communication process should be established with the participant so that the site is informed of the pregnancy test results. If a visit by site staff or home nursing staff is arranged, it is important that participants are instructed to perform the urine pregnancy test first and only if the test result is negative proceed with the administration of the study treatment.

Safety assessments are specified below with the assessment schedule detailing when each assessment is to be performed.

For details on AE collection and reporting, refer to AE section. Please consult the Investigator's Brochure for the specific (non-routine) safety assessments.

Table 8-2 Safety Assessment

Assessment	Specification
Physical	A complete physical examination will include the examination of general appearance, skin, neck (including thyroid), eyes, ears, nose, throat, lungs, heart, abdomen, back, lymph nodes, extremities, vascular, and neurological. If indicated based on medical history and/or symptoms, rectal, external genitalia, breast, and pelvic exams will be performed.
	A short physical exam will include the examination of general appearance and vital signs (blood pressure [SBP and DBP] and pulse). A short physical exam will be at all visits starting from visit 3 except where a complete physical examination is required (see above).
	Information for all physical examinations must be included in the source documentation at the study site. Clinically relevant findings that are present prior to signing informed consent must be recorded on the appropriate CRF that captures medical history. Significant findings made after signing informed consent which meet the definition of an Adverse Event must be recorded as an adverse event.

Vital signs	Vital signs include BP and pulse measurements. After the participant has been sitting for five minutes, with back supported and both feet placed on the floor, systolic and diastolic blood pressure will be measured three times using a validated device, e.g. standard sphygmomanometer or an automated BP device, with an appropriately sized cuff. The repeat sitting measurements will be made at 1-2 minute intervals and the mean of the three measurements will be used. In case the cuff sizes available are not large enough for the participant's arm circumference, a sphygmomanometer with an appropriately sized cuff may be used.
Height and weight	Height in centimeters (cm) and body weight (to the nearest 0.1 kilogram (kg) in indoor clothing, but without shoes) will be measured.

8.4.1 Laboratory evaluations

Specimens will be obtained at the time points in the Assessment Schedule (Table 8-1).

A central laboratory will be used for analysis of all specimens collected, with the exception of urine pregnancy tests and urine dipstick tests, which will be done locally at the site (using testing materials supplied by the central laboratory). Serum pregnancy tests at screening will be done by the central laboratory. Details on the collections, shipment of samples and reporting of results by the central laboratory are provided to investigators in a Laboratory Manual.

In case of abnormal dipstick urinalysis results, microscopy and other assessments (e.g. serum albumin and serum total protein) will be performed at the local laboratory and the abnormality recorded as an AE.

Clinically significant abnormalities must be recorded as either medical history/current medical conditions or adverse events as appropriate.

Clinically notable laboratory findings are defined in Section 16.1

Local laboratory assessments may be performed on an as-needed basis for unscheduled visits. Laboratory values that exceed the boundaries of a notable laboratory abnormality must be commented on by the investigator on the source document and additional laboratory evaluations should be performed, as judged appropriate by the investigator. If the laboratory abnormality induces clinical signs or symptoms, or requires therapeutic intervention, then the diagnosis or medical condition must be entered on the patient's AE eCRF. If the laboratory abnormality is the primary reason for an unforeseen hospitalization or otherwise fulfills the seriousness category of an AE, then the procedure for rapid notification of SAEs must be followed. Likewise, if the laboratory abnormality leads to discontinuation from the study drug (temporarily or permanently), the patient must be followed until the abnormality resolves or until it is judged to be permanent. This investigation may include continued monitoring by repeat laboratory testing or by performing additional laboratory tests as deemed necessary by the investigator or the Novartis medical monitor.

As per Section 4.6, during a Public Health emergency that limits or prevents on-site study visits, if a visit by site staff/home nursing staff is arranged, specimen samples should be collected during the visit and processed and handled in line with the study laboratory manual.

Table 8-3 Clinical Laboratory Assessments

Test Category	Test Name
Hematology	Hematocrit, Hemoglobin, MCH, MCHC, MCV, Platelet count, White blood cell count with Differential (Basophils, Eosinophils, Lymphocytes, Monocytes, Neutrophils, Bands, Other)
Chemistry	Full serum chemistry: Albumin, Alkaline phosphatase (ALP), ALT, AST, Gammaglutamyl-transferase (GGT), Lactate dehydrogenase (LDH), Bicarbonate, Calcium, Magnesium, inorganic Phosphate, Chloride, Sodium, Potassium, Creatinine, estimated Glomerular Filtration Rate (eGFR), Creatine kinase (CK), Direct Bilirubin, Indirect Bilirubin, Total Bilirubin (TBL), Total Cholesterol, LDL-C (direct), VLDL, HDL-C. Apolipoprotein B, Total Protein, Triglycerides, Blood Urea Nitrogen (BUN) or Urea, Uric Acid, Amylase, Lipase, Hemoglobin A1C, Glucose (fasting) and glycated hemoglobin (HbA1C) Limited serum chemistry (ONLY): AST, ALT,
	ALP, GGT, TBL, CK, creatinine, eGFR, fasting glucose and HbA1C
Coagulation	Prothrombin Time (PT), International Normalized Ratio (INR) and Activated Partial Thromboplastin Time (aPTT)
Urinalysis	Macroscopic Panel (Dipstick) (Color, Bilirubin, Red Blood Cells/Erythrocytes, Glucose, Ketones, White Blood Cells/Leukocytes, Nitrite, pH, Protein, Specific Gravity, Urobilinogen) Microscopic Panel (only performed in the event of abnormalities) (Red Blood Cells, White Blood Cells, Casts, Crystals, Bacteria, Epithelial cells)
Hepatitis markers	HBV-DNA, HBsAg, HBsAb, HBcAb, HCV RNA-PCR (polymerase chain reaction) (screening visit)
Additional tests	Lipoprotein(a) (Lp(a))
Pregnancy Test	Serum / Urine pregnancy test

